3.3.2 Secondary Efficacy Endpoints

Blinded Phase:

The following endpoints will be compared between treatment arms over the 16-week, double-blind treatment period (all changes relative to baseline):

Key:

1. Number of patients considered treatment responders defined as those with a $\geq 50\%$ reduction in TSC-associated seizure frequency (see Section 5.1.3.7).
2. Change in Caregiver Global Impression of Change (CGIC) or Subject Global Impression of Change (SGIC) score.
3. Change in total seizures.

Other:

Antiepileptic Efficacy Measures:

- Number of patients considered treatment responders defined as those with a $\geq 25\%$, $\geq 50\%$, $\geq 75\%$ or 100% reduction in TSC-associated seizure frequency.
- Number of patients experiencing a $> 25\%$ worsening, $- 25$ to $+ 25\%$ no change, $25-50\%$ improvement, $50-75\%$ improvement or $> 75\%$ improvement in TSC-associated seizure frequency.
- Change in number of TSC-associated seizure-free days.
- Change in number of 'other' seizures (absence, myoclonic, focal sensory and infantile/epileptic spasms).

Growth and Development (in patients less than 18 years old):

- Change in serum insulin-like growth factor-1 (IGF-1) levels.
- Change in Tanner Staging score (for patients aged 10–17 [inclusive]).

Quality of Life:

- Changes in the Quality of Life in Childhood Epilepsy (QOLCE; patients 2–18 years) or Quality of Life in Epilepsy (QOLIE-31-P; patients 19+ years) score.
- Change in Physician Global Impression of Change (PGIC) score.

Safety and Tolerability:

- AEs.
- Clinical laboratory parameters.
- 12-lead electrocardiogram (ECG).
- Physical examination parameters.
- Vital signs.
- Columbia-Suicide Severity Rating Scale (C-SSRS: 19+ years) or C-SSRS Children's (6–18 years) score, where applicable.
- Number of inpatient hospitalizations due to epilepsy.
- Abuse liability.
- Effects on menstruation cycles (in females).

Open Label Extension:

The following endpoints will be assessed relative to the pre-randomization baseline of the blinded phase:

Key:

- Percentage change in number of TSC-associated seizures (average per 28 days).
- Number of patients considered treatment responders defined as those with a $\geq 50\%$ reduction in TSC-associated seizure frequency.
- Change in CGIC or SGIC score.
- Change in total seizures.

Other:

Antiepileptic Efficacy Measures:

- Number of patients considered treatment responders defined as those with a $\geq 25\%$, $\geq 50\%$, $\geq 75\%$ or 100% reduction in TSC-associated seizure frequency.
- Number of patients experiencing a $> 25\%$ worsening, $- 25$ to $+ 25\%$ no change, $25-50\%$ improvement, $50-75\%$ improvement or $> 75\%$ improvement in TSC-associated seizure frequency.
- Change in number of TSC-associated seizure-free days.
- Change in number of 'other' seizures (absence, myoclonic, focal sensory and infantile/epileptic spasms).

Growth and Development (patients less than 18 years):

- Change in serum IGF-1 levels.
- Change in Tanner Staging score (for patients aged 10–17 [inclusive]).

Quality of Life:

- Changes in the QOLCE (patients 2–18 years) or QOLIE-31-P (patients 19+ years) score.
- Change in PGIC score.

Safety and Tolerability:

- Clinical laboratory parameters.
- ECG.
- Physical examination parameters (including height and weight).
- Vital signs.
- C-SSRS (19+ years) or C-SSRS Children's (6–18 years) score, where applicable.
- Number of inpatient hospitalizations due to epilepsy.
- Abuse liability.
- Effects on menstruation cycles (in females).

3.3.3 Exploratory Endpoints (Double-blind and Open-label Extension)

Antiepileptic Efficacy Measures:

- Change in composite focal seizure score (frequency \times severity).
- Change in number of seizures by subtype.
- Change in use of rescue medication.
- Change in the number of episodes of status epilepticus (convulsive and non-convulsive).
- Changes in duration of seizure subtypes as assessed by the Subject Global Impression of Change in Seizure Duration (SGIC-SD) or the Caregiver Global Impression of Change in Seizure Duration (CGIC-SD).

TAND:

Cognitive and Behavioral Function:

- Changes in Vineland Adaptive Behavior Scales, Second Edition (Vineland-II).

- Changes in Wechsler Scales (pre-school, primary, children, adult).
- Changes in Achenbach Child Behavior Checklists (CBCL) and Adult Behavior Checklist (ABCL).

Autistic Features:

Change in Social Communication Questionnaire (SCQ) score.

PK (Double-blind only):

- The plasma concentrations will be summarized by time window for CBD and its major metabolites following single and multiple doses of GWP42003-P. Where data allows, the area under the plasma concentration curve (AUC_{0-t}) from time zero to the last measurable time-point will be calculated.
- Plasma concentrations of concomitant AEDs before and after treatment with GWP42003-P, where available.

4. BLINDED DATA REVIEW MEETING

Prior to breaking the blind, it is anticipated that a Blinded Data Review Meeting (BDRM) will take place. The objectives of the meeting will include the identification and agreement on major protocol deviations and the need for a per protocol (PP) analysis set.

The meeting will have access to the following blinded summary tables and listings:

- Pre-randomization patient data
- Patient efficacy data
- Concomitant medication data
- Patient safety data
- Patient protocol deviation logs

This SAP documents the currently planned analyses for this trial that will be approved prior to breaking the blind for the trial. Changes to the analyses planned within any previously approved versions of the SAP will be summarized in Section 7 and integrated into the text of the SAP. The minutes of the BDRM will be documented separately.

5. STATISTICAL METHODS

5.1 General Considerations

In all tables, listings and figures for the double-blind phase, the trial medications will be referred to and labelled as per Table 1.

Table 1 Blinded Phase Trial Treatments

Endpoint	Actual Treatment	Treatment Label
Efficacy	Pooled Placebo	Placebo
Safety	25 mg/kg/day Placebo	Placebo 25 mg/kg
	50 mg/kg/day Placebo	Placebo 50 mg/kg
All	25 mg/kg/day GWP42003-P	25 mg/kg
All	50 mg/kg/day GWP42003-P	50 mg/kg

For safety tables where placebo is split by dosing volume, an additional Pooled Placebo column will be included.

For OLE tables, columns will be included for treatment received during the double-blind phase (GWP42003-P or placebo, i.e. not split by dose) and overall.

In all tables, listings and figures, the trial visits will be referred to and labelled as per Table 2.

Table 2 Trial Visits

Actual Visit	Visit Label
Visit 1: Screening	Day -35
Visit 2: Day -28, baseline visit	Day -28
Visit 3: Day 1, Randomization	Day 1
Visit 4: Day 15	Day 15
Visit 5: Day 29	Day 29
Visit 6: Day 43	Day 43
Visit 7: Day 57	Day 57
Visit 8: Day 71, Telephone	Day 71
Visit 9: Day 85	Day 85
Visit 10: Day 113	End of Treatment
Visit 11: Day 123	End of Taper
Visit 12: Day 151	Safety Follow-Up
Visit B1: Day 1, Enrollment	OLE Day 1
Visit B2: Day 15	OLE Day 15
Visit B3: Day 36	OLE Day 36
Visit B4: Day 92	OLE Day 92
Visit B5: Day 141, Re-stocking of supplies	OLE Day 141
Visit B6: Day 183	OLE Day 183
Visit B7: Day 232, Re-stocking of supplies	OLE Day 232
Visit B8: Day 274	OLE Day 274
Visit B9: Day 323, Re-stocking of supplies	OLE Day 323
Visit B10: Day 365	OLE End of Treatment
Visit B11: Day 375	OLE End of Taper
Visit B12: Day 389	OLE Post-taper Safety Telephone Call
Day 403	OLE Follow-Up

Unless stated otherwise, continuous variables will be summarized showing the number of non-missing values (n), mean, standard deviation, median, minimum and maximum and categorical variables will be summarized showing the number and percentage of patients falling in each category. For continuous summaries of seizure frequency, the lower and upper quartiles will also be presented.

Minimum and maximum values will be presented to the same decimal precision as the raw data. Mean and median will be presented to one more decimal place than the raw data, and standard deviation to 2 more decimal places than the raw data. Percentages will be presented to one decimal place.

Unless otherwise specified, tables for the blinded phases will be summarized by randomized treatment arm, and for the open-label extension phase will be summarized by double-blind randomized treatment arm and overall.

All analyses and summaries will be produced using SAS Version 9.3 or higher.

5.1.1 Missing Data

5.1.1.1 Handling of Missing Data for the Primary Efficacy Endpoint

If a patient withdraws during the treatment period, then the primary analysis variable will be calculated from all the available data, during the treatment period, including any data available after the patient withdraws.

Section 5.5.2.1 describes sensitivity analyses to account for missing data arising from unreported days in the interactive voice response system (IVRS), and missing data arising from patients withdrawing during the treatment period.

5.1.1.2 Handling of Missing Data for the Secondary Efficacy Endpoints

5.1.1.2.1 Quality of Life in Childhood Epilepsy (2–18 Years)

The calculations of subscale and overall scores for the QOLCE will treat responses of 'Not Applicable' as missing values.

For each subscale, if fewer than 50% of the items within the subscale are missing (including 'Not Applicable') then the subscale score will be calculated using the mean of the non-missing items. If 50% or more of the items within the subscale are missing then the subscale score will not be calculated and will be missing.

For the overall quality of life score, if less than 8 of the 16 subscale scores are missing then the overall quality of life score will be calculated using the mean of the non-missing subscale scores. If 8 or more of the subscale scores are missing then the overall quality of life score will not be calculated and will be missing.

5.1.1.2.2 Quality of Life in Epilepsy, Version 2 (19 Years and Above)

For missing questions within subscales, the following rule will be applied:

- For subscales containing 4 or more questions (not including the 'distress' item), apply the following:
 - If less than or equal to 50% of the questions within the subscale are missing then the converted score for the missing questions will be set to the average of the non-missing question converted scores.
 - If more than 50% of the questions within the subscale are missing then the subscale weighted score will be set to missing.
- For subscales containing less than 4 questions (not including the 'distress' item) the subscale weighted score will be set to missing.

For missing 'distress' items, the following rule will be applied:

- If the corresponding subscale weighted score is missing then no imputation is needed and the 'distress' item converted score will be missing.
- If the corresponding subscale weighted score is not missing then set to the average of the non-missing 'distress' item converted scores.

For missing subscale weighted scores or missing 'distress' item converted scores, the following rule will be applied when calculating the total score:

- If 3 or more of the 'distress' item converted scores are missing then the total score will be set to missing.
- If 3 or more of the subscale weighted scores are missing then the total score will be set to missing.

- If less than 3 'distress' item converted scores are missing and less than 3 subscale weighted scores are missing, then the total score will be calculated based on the available non-missing data, following the rules above.

Note: it is possible that a subscale weighted score is missing, but that the corresponding 'distress' item was answered and the converted score is not missing. Following the rules above, the total score would include the non-missing 'distress' item converted score in the calculation even though the corresponding subscale weighted score is missing and hence not included.

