5.5.3.2.5 Quality of Life in Epilepsy, Version 2 (19 Years and Above)

Blinded Phase:

The QOLIE-31-P is a survey of health-related quality of life for adults with epilepsy. It comprises 38 questions about health and daily activities and also includes questions designed to evaluate how much distress the patient feels about problems and worries related to epilepsy. The QOLIE-31-P will be administered to patients aged 19 years or older. Should the patient be unable to complete the QOLIE-31-P independently, it is permissible for their caregiver to assist.

The questionnaire consists of the following 7 subscales: energy, mood, daily activities, cognition, medication effects, seizure worry, and overall quality of life. Each subscale consists of a number of questions in addition to a 'distress' item. The raw score for each question and the 'distress' item are converted to a 0-100 score according to the scoring manual² (higher scores reflecting greater well-being). The converted scores for each question within the subscale are then used to calculate a final subscale weighted score (higher scores reflect better quality of life; lower ones, worse quality of life) as follows:

$$\left(\frac{\text{Sum of converted scores for each question in the subscale}}{\text{Number of questions in the subscale}} + \text{'distress' item converted score} \right)$$

The total score (ranging from 0 to 100) is then calculated as:

$$\left(\frac{\text{Sum of all subscale weighted scores} + \text{Sum of all subscale 'distress' item converted scores}}{\text{Number of subscales}} \right) \times 100$$

Individual items will be listed only. The weighted subscale scores and the total score, recorded at each visit, will be summarized, on a continuous scale, by treatment arm. The change from baseline will also be included.

The change from baseline to the end of treatment visit, for the weighted subscale scores and the total score, will be analyzed using the same ANCOVA approach as specified in Section 5.5.3.2.4.

Missing data will be handled according to Section 5.1.1.2.2.

The QOLIE-31-P was to be completed for patients aged 19 years and above only. The primary analysis will be based on all patients who have a completed questionnaire, regardless of age. Summaries and analyses will be repeated using questionnaires only from patients who were aged 19 years or older at the time of informed consent.

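### The QOLIE-31-P total keeps an answered distress item when its subscale score is missing, so the total shifts for a reason that is purely missing data

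*SAP*

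**What the plan says.** SAP section 5.5.3.2.5 describes the instrument: "The questionnaire consists of the following 7 subscales: energy, mood, daily activities, cognition, medication effects, seizure worry, and overall quality of life". Each subscale also has one distress item. The total is built from the subscale weighted scores together with "Sum of all subscale 'distress' item converted scores", and its scale is given in the lead-in: "The total score (ranging from 0 to 100) is then calculated as". Its change from baseline to the end of treatment visit is analysed by ANCOVA.

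SAP section 5.1.1.2.2 sets the missing-data rules:

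- In a subscale of 4 or more questions, missing questions are imputed when up to half are missing. Beyond that: "If more than 50% of the questions within the subscale are missing then the subscale weighted score will be set to missing".
- Where a question is missing in a short subscale, nothing is imputed: "For subscales containing less than 4 questions (not including the 'distress' item) the subscale weighted score will be set to missing".
- An unanswered distress item follows its subscale: "If the corresponding subscale weighted score is missing then no imputation is needed and the 'distress' item converted score will be missing". If the subscale score is present, the distress item is imputed.
- The total is still calculated with 1 or 2 subscale scores missing.
- An answered distress item whose subscale score is missing is treated differently. The Note says that "the total score would include the non-missing 'distress' item converted score in the calculation even though the corresponding subscale weighted score is missing".

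**The concern.** The rules pair each distress item with its subscale except in one case: the distress item is answered and the subscale score is missing. Its distress score then counts in one sum while nothing from that subscale counts in the other. Two patients who lack the same subscale score are scored differently according to whether they answered its distress item.

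The SAP's rule for the sister instrument has no such gap: section 5.1.1.2.1 takes the QOLCE overall score as the mean of the subscale scores that are present.

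At stake is the ANCOVA of the QOLIE-31-P total. If a patient has every subscale score at baseline and lacks one at end of treatment, the change score contains the real change plus a shift produced by the scoring rule.

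**Working it through.** **Inputs.** From section 5.5.3.2.5: 7 subscales, one distress item each, total on 0 to 100. From section 5.1.1.2.2: 1 or 2 subscale scores may be missing. The SAP gives no typical scores, so the following are assumed: equal subscale means S from 40 to 80 and, unless stated otherwise, equal distress scores d from 25 to 75.

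**The plan's own figure, the 0 to 100 range.** As read, a weighted score is the subscale mean plus the distress score, and the total is (sum of weighted scores + sum of distress scores) / 7 × 100. With everything at 100 this gives (7 × 200 + 7 × 100) / 7 × 100 = 30,000, or 300 without the factor 100. The stated range is not reproduced. The layout may have been damaged in extraction, so the effect was worked out under two readings.

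**Reading 1: distress items as weights (assumed).** Weighted score = S × d / 100; total = sum of weighted scores / sum of distress scores × 100. With everything at 100 this gives 100, so the range fits. If subscale k is missing and its distress score is kept, the shift is -(d_k / sum of d) × S_k. With equal distress scores, one missing subscale multiplies the total by 6/7:

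- S = 40: 40.0 becomes 34.3 (-5.7)
- S = 60: 60.0 becomes 51.4 (-8.6)
- S = 80: 80.0 becomes 68.6 (-11.4)

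Two missing at S = 60: 60 × 5/7 = 42.9 (-17.1).

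The kept distress score matters. With S = 60 and the other six distress scores at 50, the shift is -60 × d_k / (300 + d_k). For d_k = 0, 25, 50, 75 and 100 this is 0, -4.6, -8.6, -12.0 and -15.0.

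**Reading 2: printed sums, divided by 3 to bring the maximum of 300 to 100.** The complete total is (S + 2d) / 3. With one subscale missing and its distress score kept:

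- Divisor 7: shift = -(S + d) / 21, from -65/21 = -3.1 (S = 40, d = 25) to -155/21 = -7.4 (S = 80, d = 75).
- Divisor 6: shift = +d / 18, from 25/18 = +1.4 to 75/18 = +4.2.

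**Effect of pairing, at S = 60 and d = 50:**

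| Reading | Complete | One missing, distress kept | One missing, distress also left out |
|---|---|---|---|
| Weights | 60.0 | 51.4 | 60.0 |
| Printed sums, divisor 7 | 53.3 | 48.1 | 45.7 |
| Printed sums, divisor 6 | 53.3 | 56.1 | 53.3 |

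The 45.7 is (6 × 110 + 6 × 50) / 7 / 3. Under the printed sums, therefore, leaving out the distress item restores the total only if the divisor also drops to 6.

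**Unequal scores.** A simulation of Reading 1 (assumed subscale mean 60, SD 20, distress scores 0 to 100 in steps of 25) gave an average shift of -8.5 under the Note and 0.0 with paired omission. Individual totals still vary after pairing, because the lost subscale may differ from the others, but the systematic shift is gone.

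**The case against.** Several stronger readings are tempting, and the SAP does not support them.

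- *Any skipped question moves the total.* It does not. Longer subscales are imputed up to half missing, and the distress item of the lost subscale must have been answered. The SAP says of the questionnaire that "It comprises 38 questions about health and daily activities" but never gives the number per subscale. Which subscales are short, and how often this would occur, cannot be read from it.
- *The total falls by a fixed amount.* Size and even sign depend on a formula that cannot be read with certainty. Section 5.1.1.2.2 bases the total on the available non-missing data, which arguably points to divisor 6 and the smaller, upward shift. With a kept distress score near 0 the effect nearly vanishes under the weights reading and under divisor 6.
- *The treatment comparison is biased.* The rule is prespecified, disclosed and the same in every arm and at every visit. Missingness unrelated to arm mainly adds noise, and the same gap at both visits partly cancels. The SAP gives no reason to expect missing items to differ by arm.
- *The printed formula is an error in the plan.* It may be an artefact of extraction, so it calls for a check only.

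It is also fair that the scoring follows a cited manual that is not at hand, and that the Note may come from it. All of this limits the reach of the point. None of it removes the mismatch, which the Note states in plain prose and which shifts the total under each reading tried.

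**Conclusion.** The point holds in this limited form. When a subscale score is missing and its distress item was answered, the Note makes the two parts of the total cover different subscales. With one subscale missing the shift is about -6 to -11 points under the weights reading. Under the printed sums rescaled to 0 to 100 it is about -3 to -7 with divisor 7, or +1 to +4 with divisor 6. These figures rest on assumed equal scores and on an uncertain formula; the existence of a shift rests only on the Note.

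The consequence is minor. The QOLIE-31-P is listed among the other secondary endpoints (section 3.3.2), is meant for patients aged 19 and above, and is outside the testing sequence in Table 3. The subscale scores, which are analysed separately, are not touched by the Note, and the primary and key secondary results are unaffected.

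**What to change.** Replace the Note in section 5.1.1.2.2 with a rule that, whenever a subscale weighted score is missing, its distress item is also left out of the total, and any count of subscales in the divisor covers only those used. Keep the present limit of fewer than 3 missing.

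Check the total formula in section 5.5.3.2.5 and this rule against the cited scoring manual. If the manual requires the Note's rule, keep it for the main derivation and report the paired-omission total as a sensitivity analysis.

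The cost is one sentence in the SAP and one line of derivation code, plus one extra ANCOVA if the sensitivity route is taken.

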5.1.1.3 Adverse Events

Missing and/or incomplete dates/times for AEs will be imputed in a manner resulting in the earliest onset or the longest duration during the treatment period, taking into account that the start date/time should not be after the stop date/time. Stop dates/times will not be imputed if the AE is ongoing.

The imputation method will only be used to determine treatment emergence, and imputed dates/times will not be presented in AE outputs.

A worst-case approach will be followed in the event of missing severity or causality data. If the severity is missing, 'Severe' will be imputed. If causality data is missing, 'Yes' will be imputed for the question 'Plausible relationship to study medication'.

5.1.1.4 Concomitant Medication

Missing concomitant medication dates will be handled in a similar fashion as described for AEs in Section 5.1.1.3.

5.1.2 Day Numbering

Blinded Phase:

The first day of treatment (Day 1) will be taken from the Study Medication case report form (CRF) page at Visit 3. However, if this date is missing then the date of Visit 3 will be used.

Any days prior to Day 1 will be numbered relative to this day and calculated as:

Date - (Date of Day 1); to give Day -1, -2, -3 etc.

Any days post Day 1 will be calculated as:

1 + Date - (Date of Day 1)

Open-label Extension:

The first day of treatment in the OLE (OLE Day 1) will be day of entry into the OLE, which is expected to be the same day as the end of treatment visit from the blinded phase. OLE day will be calculated as above but relative to OLE Day 1.

